8.2.2 Power and Sample Size Calculations for Immunogenicity

The precision and power calculations for safety shown in Table 4 and Table 5 also apply to immunogenicity results. Results of immunogenicity assessments can be shown as proportion of responders (Table 4 applied) or continuous measures (Table 5 applied). For example, if we observe 10 positive responses from an ELISA assay in an individual group, the 95% exact confidence interval of the true response rate will range from 0.272 to 0.728. Note that immunogenicity is a secondary objective for this protocol.

8.3 Statistical Analysis

All analyses will be described overall and by vaccination group (Group 1 and Group 2). The safety and immunogenicity analysis will include all vaccinated participants. All statistical analyses will be performed using Statistical Analysis System (SAS), R, or S-Plus statistical software. No formal multiple comparison adjustments will be employed for safety endpoints or secondary endpoints.

8.3.1 Baseline Demographics

Baseline demographics and laboratory measurements will be summarized for individual groups and overall. Categorical variables will be reported in numbers and percents with exact 95% Clopper-Pearson confidence intervals. Continuous variables will be reported in means and standard deviations or medians and IQR as appropriate.

8.3.2 Safety Analysis

Safety and tolerability will be assessed by both clinical and laboratory monitoring. If comparisons are performed between groups, then Barnard's exact unconditional test will be performed for binary variables and t-tests (or Wilcoxon Rank Sum as appropriate) for continuous measures.

Reactogenicity

The number and percentage of participants experiencing each type of reactogenicity sign or symptom will be tabulated by study group and severity. Exact 95% Clopper-Pearson confidence intervals will be calculated for each set of events. For a given sign or symptom, each participant's reactogenicity will be counted once under the maximum severity for all assessments.

Adverse Experiences

Adverse experiences are coded into Medical Dictionary for Regulatory Activities (MedDRA) system organ classes and preferred terms. The number and percentages of participants experiencing each specific adverse event will be tabulated by dose level, severity and relationship to treatment. For the tabulation of the adverse experiences by system organ class, a participant was counted only once in a given body system. For example, a participant reporting gastritis and diarrhea will be reported as one participant, but the symptoms will be listed as two separate AEs within the class. A complete listing of adverse experiences for each participant will provide details including preferred term, system organ class, severity, relationship to treatment, onset time, duration and outcome.

Local Laboratory Values

Boxplots of local laboratory values will be generated for baseline values and for values measured during the course of the study. Each boxplot will show the 1st quartile, the median, and the 3rd quartile. Outliers, or values outside the boxplot, will also be plotted. If appropriate, horizontal lines representing boundaries for abnormal values will be plotted. Tables will be provided for changes from baseline.

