It is anticipated that about 100 volunteers will be screened in order to enroll a total of 40 participants. The 40 participants will be evenly split, with 20 in each of the two dosage groups for cAd3-EBO S. The dose escalation plan includes daily review of any new safety data by a study clinician, regular review of safety data by the protocol team and a staged enrollment plan with required interim safety reviews. The study will begin with enrollment of 3 participants into Group 1 at a rate of 1 participant per day. After at least 7 days of follow-up for the first 3 vaccinated participants, an interim safety review will occur before enrollment of additional participants into the group. If no safety issues are identified, an additional 17 participants will be enrolled to complete Group 1. When there is a minimum of seven days of follow-up safety data from the last enrolled participant in Group 1, an interim safety review will occur. Once no safety issues are identified, enrollment of participants into the next dose level (Group 2) will begin with the enrollment of 3 participants at a rate of 1 participant per day. After at least 7 days of follow-up for the first 3 vaccinated participants in Group 2, an interim safety review will occur before the enrollment of additional participants into Group 2. If no safety issues are identified, an additional 17 participants will be enrolled to complete Group 2.

Product Description

VRC-EBOADC086-00-VP (cAd3-EBO S) is composed of a cAd3 vector that expresses Ebola Sudan WT GP. It is formulated at 1×10^{11} PU/mL.

VRC-DILADC065-00-VP (diluent) is the formulation buffer used for vaccine production and will be used when needed to prepare the 1×10^{10} PU/mL dose of cAd3-EBO S.

Participants

Healthy adults in the Kampala area aged 18-50 years will be enrolled.

Study Duration

Participants will be evaluated at 9 clinic visits over 48 weeks.

Study Objectives

Primary Objectives

- To evaluate the safety and tolerability of VRC-EBOADC086-00-VP when administered IM at a dose of 1×10^{10} particle units (PU) to healthy adults;
- To evaluate the safety and tolerability of VRC-EBOADC086-00-VP when administered IM at a dose of 1×10^{11} PU to healthy adults.

Secondary Objectives

- To evaluate the antibody response to the GP insert and cAd3 vector in VRC-EBOADC086-00-VP at 4 weeks after vaccination as assessed by GP ELISA and vector-specific neutralization assays, respectively.

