3.0 ENDPOINTS

3.1 Primary Endpoints: Safety

Assessment of product safety will include clinical observation and monitoring of clinical chemistry and hematology parameters. Safety will be closely monitored after injection and evaluated through 48 weeks after the study injection. The following parameters will be assessed:

- Occurrence of solicited local reactogenicity signs and symptoms for 7 days following the vaccination
- Occurrence of solicited systemic reactogenicity signs and symptoms for 7 days following the vaccination
- Change from baseline for safety laboratory measures
- Occurrence of adverse events of all severities through 28 days after the study injection
- Occurrence of serious adverse events and new chronic medical conditions through the last study visit

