Study volunteers may be scheduled for a second Screening Visit to evaluate laboratory and test results if an abnormality or illness had been identified at the first screening. This approach will allow study staff to evaluate the recovery from any illness identified at the first screening as well as to repeat screening laboratory tests that were abnormal at the first screen due to transient illness.

The PI or Investigator at the site may discover an illness or condition, which requires treatment for the volunteer. The site will provide basic care and treatment as per National guidelines and refer these subjects to an appropriate healthcare facility for further evaluation and treatment.

Eligible and willing volunteers will be scheduled for an appointment for enrollment and the initial vaccination visit within 56 days of having satisfied eligibility requirements.

5.2.2 Day 0 Through Week 48

Day 0 is defined as the day of enrollment and study injection. Study eligibility criteria are reviewed on Day 0 as part of the enrollment process. If clinical assessment on Day 0 suggests significant changes may have occurred since the screening visit, then the physical examination, hematology tests, and blood chemistries done at screening must be repeated, as appropriate, before the participant can receive a study vaccination. Pregnancy test results for women of childbearing potential must be obtained prior to the study injection. Day 0 evaluations immediately prior to the first injection are the baseline for subsequent safety assessments.

Refer to the table in Appendix 1 for details on the Schedule of Evaluations and the window(s) permitted. After Day 0, deviations from the visit windows in completing study visits are discouraged and will be recorded as protocol deviations, but are permitted, at the discretion of the PI (or designee), in consultation with the sponsor, in the interest of obtaining participant safety and immunogenicity evaluations following exposure to the investigational vaccine.

Study visit procedures and tests through Week 48 include the following as indicated in the SOE (Appendix 1):

1. Signature of study participation informed consent form
2. AOU (prior to enrollment)
3. Clinical evaluations: vital signs; targeted physical examination on any visit if indicated by interim complaints or laboratory findings
4. Interim medical history, including any new medications taken

5. Counseling on avoidance of pregnancy

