8.2 Sample Size and Accrual

8.2.1 Power and Sample Size Calculations for Safety

The goal of the safety evaluation for this study is to identify safety concerns associated with vaccination. Occurrence of solicited local and systemic reactogenicity symptoms, occurrence of adverse and serious adverse events will be assessed as the proportion of participants experiencing such safety event. Table 4 below shows 95% confidence intervals for 0, 1, 2, 5, and 10 participants with observed events in each group or among all study participants.

Table 4. Exact 95% Confidence Intervals for the Proportion of Participants Experiencing a Safety Event

Group	Sample Size	Number of Participants with an Event(s) Observed				
		0	1	2	5	10
Each Individual Study Group	20	0% (0%-16.8%)	5% (0.1%-24.9%)	10% (1.2%-31.7%)	25% (8.6%-49.1%)	50% (27.2%-72.8%)
All participants	40	0% (0%-8.8%)	2.5% (0.06%-13.2%)	5% (0.6%-16.9%)	12.5% (4.2%-26.8%)	25% (12.7%-41.2%)

If no participants experience an event, the upper limit of a two-sided exact 95% CI would be 16.8% for an individual group and 8.8% for the entire study group. While this study is not necessarily powered to detect differences between groups, we would have 82% power to detect a difference of 40% ($p_1=0.1$ and $p_2=0.50$) using Barnard's exact unconditional test at a 5% two-sided level of significance.

Changes in laboratory measures from baseline will also be described. For continuous safety measures, Table 5 below shows minimum detectable changes from baseline to a specified time point using a paired t-test with a two-sided 5% level test.

Table 5 Minimum Detectable Differences, in Standard Deviations, for Change From Baseline to a Single Time (2-sided $\alpha=0.05$)

Group	Sample Sizes	Power		
		80%	85%	90%
1 (1×10^{10} PU/mL)	15	0.78	0.83	0.9
2 (1×10^{11} PU/mL)	20	0.66	0.71	0.76
All Active	35	0.49	0.52	0.56

If comparing the two study groups, we would have 80% power to detect a difference of 0.91 standard deviations using a two-sample t-test with a two-sided 5% alpha and assuming equal variances.

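### Any between-dose comparison of a laboratory safety measure is left to a t-test or Wilcoxon on an unnamed quantity; a model that includes the Day 0 value would usually be more efficient

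*Combined protocol and SAP*

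**What the plan says.** All references are to the combined protocol and SAP.

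- Section 3.1 lists as a primary safety endpoint "Change from baseline for safety laboratory measures".
- Section 5.2.2 fixes the reference point: "Day 0 evaluations immediately prior to the first injection are the baseline for subsequent safety assessments". The schedule in Appendix 1 draws CBC, creatinine and ALT on Day 0 and again on Days 3, 7, 14, 28 and 56.
- Section 8.3.2 makes between-group safety comparisons conditional. If they are made, continuous measures get "t-tests (or Wilcoxon Rank Sum as appropriate) for continuous measures". Laboratory results are otherwise shown as boxplots and tables of change.
- Section 8.2.1 says that the study is not necessarily powered for group differences. After the table of detectable changes from baseline it adds: "we would have 80% power to detect a difference of 0.91 standard deviations using a two-sample t-test with a two-sided 5% alpha", "assuming equal variances".

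Neither 8.2.1 nor 8.3.2 says whether the two-sample test, or the SD in which 0.91 is expressed, refers to the change or to the post-vaccination value. No visit is named for the comparison, and no correlation between Day 0 and follow-up is given.

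**The concern.** With 20 participants per dose, a between-dose contrast has little precision to spare. The participant's own Day 0 value of the same analyte is often the best available predictor of the follow-up value, and it is already being collected. A raw-value t-test discards it. A change-score t-test uses it with a fixed coefficient of 1, which is more than the regression slope whenever the correlation is below 1 and the variances are equal. A model that estimates the coefficient usually leaves less residual variance.

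Leaving the compared quantity open also means that the choice between change and raw value, and the choice of visit, could be made after the data are seen. At stake are the width of the interval for an optional dose contrast and its pre-specification. The validity of the main safety description is not at stake.

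**Working it through.** **Inputs.** From the documents: 20 per group (Schema and section 4.0: "The 40 participants will be evenly split, with 20 in each of the two dosage groups for cAd3-EBO S"), 0.91 SD, two-sided 5%, equal variances (8.2.1). Assumed: the correlation ρ between Day 0 and follow-up, and equal variance σ² at the two times.

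**The plan's own figure.** Noncentrality = 0.91 / √(1/20 + 1/20) = 0.91 / 0.3162 = 2.878, with 38 df. Power is 80.1% and the detectable difference at 80% power is 0.909 SD. The stated figure reproduces. It needs 20 per group: with the 15 and 20 printed in Table 5, power at 0.91 SD would be 73.4% and the detectable difference 0.986 SD. That mismatch in sample size is a separate point.

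**Gain if 0.91 is in SDs of the change.** Var(change) = 2σ²(1−ρ). The residual variance after adjusting for Day 0 is σ²(1−ρ²). The ratio is (1+ρ)/2, so the standardised effect becomes 0.91 / √((1+ρ)/2), with 37 df.

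| ρ (assumed) | Variance ratio | Effect | Noncentrality | Power | Detectable at 80% |
|---|---|---|---|---|---|
| 0.5 | 0.75 | 1.051 | 3.323 | 89.9% | 0.79 SD |
| 0.7 | 0.85 | 0.987 | 3.121 | 86.0% | 0.84 SD |
| 0.9 | 0.95 | 0.934 | 2.952 | 82.0% | 0.89 SD |

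The gain over the plain test is about 10, 6 and 2 points.

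**Gain if 0.91 is in SDs of the post-vaccination value and the test is on raw values.** The ratio is 1−ρ². Power with adjustment is 80.0% (ρ = 0), 83.6% (0.3), 89.9% (0.5) and 97.5% (0.7).

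**Cost of a second covariate.** Adding sex takes the df from 37 to 36. I recomputed the first table with 36 df, and power falls by less than 0.1 point in each row. This credits sex with explaining nothing beyond Day 0.

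**Baseline imbalance.** The formulas above take the groups as balanced on Day 0. A gap of D baseline SDs multiplies the variance of the adjusted difference by 1 + D² / (38 × 0.1). At D = 0.5 this is 1 + 0.25/3.8 = 1.066. Power on the change reading is then 83.7% (ρ = 0.7), 81.6% (0.8) and 79.5% (0.9).

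**Bias check by simulation (all inputs assumed).** No dose effect, sex mix 14/6 against 6/14, a 1.5-unit sex difference in level, within-sex SD 0.7, measurement SD 0.6. False-positive rates at a nominal 5%:

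- change-score t-test: about 5%;
- model on dose and Day 0 only: about 9%, with a bias of −0.16 units;
- model on dose, Day 0 and sex: about 5%.

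When the sex mix differs only by chance, the Day 0 model holds 5% and has more power than the change score.

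**The case against.** The strongest reply has four parts.

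- **The endpoint is already a change from baseline.** A t-test on it uses every participant's Day 0 value, and the 0.91 SD sentence follows a table about change. This stands. A reader might infer that the primary laboratory endpoint is analysed with no regard to baseline, or that the 80% is wrong. The documents support neither. What remains is an efficiency point on the change reading, plus the silence about which reading applies.
- **Nothing committed is harmed.** The comparison is conditional, its power is disclaimed, and the primary objectives evaluate each dose separately. This also stands, and it limits the weight of the point.
- **The groups are not randomised.** Group 2 opens only after Group 1 is full and reviewed. If the groups differ in a stable trait such as sex mix, a change score removes that level difference, while adjusting for Day 0 alone leaves part of it as an apparent dose effect. The simulation confirms this. Adding sex cured it in that example, but other stable differences could remain. The objection therefore alters the model and justifies keeping the change-score test beside it. It does not remove the case for adjustment.
- **The gain is assumed.** It depends on ρ, and with ρ = 0.9 and a 0.5 SD baseline gap the adjusted model falls slightly below the plain test. This is correct, so no single higher power can be claimed.

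**Conclusion.** The point holds as a modest one about efficiency and pre-specification. If a between-dose laboratory comparison is made, the plan offers only a t-test or Wilcoxon on an unspecified quantity. On change scores that is valid but usually less efficient than a baseline-adjusted model: 80% power against about 90%, 86% and 82% for ρ of 0.5, 0.7 and 0.9. On raw values it ignores Day 0. These figures rest on 20 analysed per group, equal variances at both times, an assumed ρ and near-balanced baselines.

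A reader might go further and say that the trial is underpowered on a primary endpoint, or that the same data are certain to give more power. The documents do not support this. The 0.91 SD is right for the named test, the contrast is optional and secondary to a descriptive aim, and the gain can vanish at high ρ with an imbalanced baseline.

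**What to change.** - **Section 8.3.2.** State that any between-dose comparison of a continuous safety laboratory measure is made at a named visit. It uses a linear model of the post-vaccination value on dose group, the participant's Day 0 value and sex, with a transformation if the measure is skewed, and is reported as an adjusted difference with a 95% confidence interval. Keep the change-score t-test or Wilcoxon as a sensitivity analysis, because the groups are sequential and not randomised. If the two disagree, report both.
- **Section 8.2.1.** Say whether 0.91 is in SDs of the change or of the post-vaccination value, and that it is the figure without covariate adjustment.

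The cost is a few sentences and two degrees of freedom. No new data are needed, since Day 0 values and sex are already recorded. The contrast remains non-randomised, and adjustment does not remove calendar-time or other unmeasured differences between the groups.

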8.3.3 Immunogenicity Analysis

Immunogenicity analysis will consist of all vaccinated participants. If assay data are qualitative (i.e., positive or negative) then analyses will be performed by tabulating the frequency of positive response for each assay at each time point that an assessment is performed. Binomial response rates will be presented with their corresponding exact 95% confidence interval estimates. Barnard's unconditional exact tests will be used to compare the two groups to each other. For quantitative results, mean and standard deviation will be calculated. One-sample t-tests will be used to assess the changes from baseline. Two-sample t-tests will be used to compare the two study groups. Missing responses will be assumed to be missing at random, i.e., conditional on the observed data the missingness is independent of the unobserved responses. Graphical descriptions of the longitudinal immune responses will also be given.

Some immunologic assays have underlying continuous or count-type readout that is often dichotomized into responder/non-responder categories. For these assays, graphical and tabular summaries of the underlying distributions will be made. These summaries may be performed on transformed data (*e.g.*, log transformation) to better satisfy assumptions of symmetry and homoscedasticity.

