Each clinical trial has contributed to product development and a better understanding of human immune responses to filovirus antigens. The first investigational vaccine study, VRC 204, was initiated in 2003. This was a 3-plasmid recombinant DNA vaccine, VRC-EBODNA012-00-VP, that encoded for nucleoprotein (NP) from the Zaire strain of Ebola and for transmembrane deleted (Δ TM) Ebola GP sequences from both Zaire and Sudan strains. At that time, deletion of the TM region of the GP was included in the vaccine construct design to address theoretical concerns related to cellular toxicity that had been observed during in vitro experiments when plasmids expressing full length, WT GP proteins were transfected into cell culture [26].

The second investigational vaccine study, VRC 205, evaluated a replication-defective, recombinant adenovirus serotype 5 vaccine, VRC-EBOADV018-00-VP (Ebola-rAd5). The constructs in this vaccine encoded GP genes with a point-mutation [aspartic acid substituted for glutamic acid at position 71 (E71D)], which had been found to be safe and immunogenic in animal studies. The vaccine induced humoral and T cell responses to the point mutant GP inserts with a single vaccination, but pre-existing immunity to the Ad5 virus partially blunted antibody responses to the rAd5-expressed antigen [21]. Because complete protection in macaques vaccinated with this Ebola-rAd vaccine encoding for E71D GP (Z) combined with E71D GP (S) was demonstrated, the vaccine was further evaluated in people (VRC 205) [27].

Non-human primate (NHP) studies, ongoing in parallel with the conduct of these human clinical trials, demonstrated that Δ TM GP- and PM GP-expressed antigens were partially protective against Ebola virus infection, but WT GP constructs provided the highest level of protection [27]. Therefore, the WT GP antigen became the focus of Ebola vaccine research and development at VRC/NIAID.

The third investigational Ebola vaccine to undergo NHP evaluation, VRC-EBODNA023-00-VP (Ebola DNA WT), was a recombinant DNA vaccine composed of 2 plasmids, each encoding for the wild type (WT) GP of the Zaire or Sudan strain of Ebolavirus. At the same time, a DNA

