4.0 STUDY DESIGN AND POPULATION

This is a Phase I open-label, dose-escalation clinical trial to evaluate the safety, tolerability and immunogenicity of a recombinant vector for the Sudan strain of the Ebola virus. This study will be conducted at the MUWRP in Kampala, Uganda.

A total of 40 healthy adults, 20 in each dosage group, will receive a single vaccine injection of cAd3-EBO S at 1×10^{11} PU/mL or 1×10^{10} PU/mL. The study will begin with enrollment of 3 participants into Group 1. After at least 7 days of follow-up for the first 3 vaccinated participants, an interim safety review will occur before enrollment of additional participants into the group. If no safety issues are identified, an additional 17 participants will be enrolled to complete Group 1. When there is a minimum of seven days of follow-up safety data from the last enrolled participant in Group 1, an interim safety review will occur. Once no safety issues are identified, enrollment of participants into the next dose level will begin with the enrollment of 3 participants. After at least 7 days of follow-up for the first 3 vaccinated participants in Group 2, an interim safety review will occur before enrollment of additional participants into Group 2. If no safety issues are identified, an additional 17 participants will be enrolled to complete Group 2. For the first 3 participants in each group, only one participant per day will be enrolled. The study groups and vaccination schema is shown in Table 1.

Study agent administration will be on Day 0. The study includes daily review of any new safety data by a study clinician and weekly review of safety data by the Protocol Safety Review Team (PSRT). The staged enrollment plan and plan for interim safety reviews (Section 7.3) applies to both Group 1 and Group 2. The interim safety reviews will be conducted by the PSRT.

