5.2.1 Consent Procedures and Screening

The PI or their designee will review the consent form in detail with potential participants and answer any questions. Written informed consent will be obtained from each participant before any study procedures are performed. All informed consent forms will be administered individually, in a private setting, with strict respect of confidentiality. Participants will be given ample time and opportunity to inquire about details of the study, discuss with close family members or friends and ask any questions before dating and signing the consent forms. A copy of the signed informed consent form will be given to the participant along with a copy of the volunteer event schedule (Appendix 3). The consenting process will be documented in the case report forms (CRFs).

After providing signed informed consent the volunteer will complete an Assessment of Understanding (AoU). Volunteers are allowed to take the AOU three times, but must have a passing score of 90% or greater by the third attempt to participate in the study. If after 3 attempts to pass the AOU the volunteer is unable to do so, the volunteer will become ineligible for study participation.

Volunteers who have passed the AoU and have given written informed consent will undergo a complete medical history, physical examination, and screening laboratory assessments to determine eligibility for trial participation. The following screening assessments will be completed after the informed consent process has been completed:

- Medical history
- Physical exam
- Vital signs and weight
- Serum pregnancy test for all females
- CBC with total lymphocyte count
- Creatinine
- ALT

- HIV testing (including pre/post-test counseling), and referral as appropriate
- Syphilis serology testing
- Pre-existing vector immunity testing
- Peripheral blood mononuclear cells (PBMC) and plasma for storage

Screening evaluations for specific eligibility criteria must be completed within the screening visit window specified (Appendix 1) prior to enrollment, but may be repeated one time within the screening visit window, if the initial laboratory result is not deemed medically significant in the clinical judgment of the investigator, in order to confirm eligibility. Counseling on the potential risks of becoming pregnant during this trial will be provided. Pre-HIV test counseling and post-HIV test counseling will be provided during the screening process.

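### The Week 4 dose comparison of GP responses is an unadjusted test between sequential, non-randomised cohorts, and the cAd3 antibody measured at screening has no stated role in it

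*Combined protocol and SAP*

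**What the plan says.** Section 4.0 describes the trial so: "This is a Phase I open-label, dose-escalation clinical trial". It enrols "A total of 40 healthy adults, 20 in each dosage group". Group 2 opens only after Group 1 is full, its last participant has at least 7 days of follow-up, and a safety review has been passed: "Once no safety issues are identified, enrollment of participants into the next dose level will begin with the enrollment of 3 participants". No randomisation is described.

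For quantitative immunogenicity results, section 8.3.3 states: "Two-sample t-tests will be used to compare the two study groups". Responder rates are compared by Barnard's test. Neither test has a covariate. Both comparisons are firm commitments, whereas section 8.3.2 makes between-group safety comparisons conditional.

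The screening list in section 5.2.1 includes "Pre-existing vector immunity testing", and Appendix 1 schedules it at Visit 01 only. The result is not an eligibility criterion in section 4.1, and section 8.3 does not mention it. Section 9.1.1 says that cAd3 neutralising antibody before and after vaccination will be evaluated, without naming an analysis.

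On the effect of vector immunity, section 1.2.1 reports for the earlier rAd5 Ebola vaccine that "pre-existing immunity to the Ad5 virus partially blunted antibody responses to the rAd5-expressed antigen". For cAd3, sections 1.2.1 and 1.2.2 report little pre-existing immunity, low seroprevalence, low titres when present, and no apparent cross-reaction of Ad5 immunity in mice. They give no prevalence figure, and none for Uganda.

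**The concern.** Dose is completely tied to enrolment order. Nothing in the design balances the cohorts at baseline, so a Week 4 difference may reflect dose, a difference between the people recruited early and late, or both. The t-test in 8.3.3 attributes all of it to dose, and the plan carries no caveat.

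Anti-vector antibody is a plausible baseline factor for the response to a vectored vaccine, and here it is measured in every participant before vaccination. If the high-dose cohort had more pre-existing cAd3 antibody and that antibody reduced the response, a real dose effect could be masked. If the low-dose cohort had more, a dose effect could be exaggerated or created. Section 8.3.4 says that immunogenicity results may inform later vaccine decisions, so a statement about dose could be acted on.

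**Working it through.** **1. The plan's own figures.** Section 8.2.1 states "we would have 80% power to detect a difference of 0.91 standard deviations using a two-sample t-test with a two-sided 5% alpha", and section 8.2.2 carries the safety power figures over to immunogenicity. With n = 20 per group and 38 df, the detectable difference is approximately (t₀.₉₇₅ + t₀.₈₀) × √(1/20 + 1/20) = (2.024 + 0.851) × 0.316 = 0.909 SD. The exact noncentral-t calculation also gives 0.909, so the stated 0.91 is reproduced. Section 8.2.1 also says "we would have 82% power to detect a difference of 40" percentage points (10% against 50%). Full enumeration of Barnard's test gives 82.2%. No power figure is wrong on this point.

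**2. What an imbalance would do.** The documents give neither cAd3 seroprevalence nor the size of any blunting, so both are assumed. Let p₁ and p₂ be the seropositive fractions in Groups 1 and 2, g the blunting in SD, and 1 the outcome SD within serostatus.

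- Bias in the high-minus-low difference = −(p₂ − p₁) × g
- Variance in a group = 1 + p(1 − p)g²
- Noncentrality with no dose effect = |bias| / √((v₁ + v₂)/20)

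For 10% against 30% with g = 1.0: bias = −0.20, v₁ = 1.09, v₂ = 1.21, noncentrality = 0.20/√0.115 = 0.59. With g = 0.5: bias = −0.10, v₁ = 1.0225, v₂ = 1.0525, noncentrality = 0.10/√0.10375 = 0.31.

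Simulation of the unadjusted t-test (40,000 replicates per scenario, 20 per group):

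| Prevalence, Group 1 vs Group 2 | Bias (SD), g = 0.5 / 1.0 | Type I error, g = 0.5 / 1.0 | Power at a true 0.91 SD, g = 0.5 / 1.0 |
|---|---|---|---|
| 5% vs 5% | 0 / 0 | 5.0% / 5.0% | 80% / 78% |
| 5% vs 15% | −0.05 / −0.10 | 5.5% / 5.9% | 74% / 67% |
| 10% vs 30% | −0.10 / −0.20 | 5.9% / 8.9% | 69% / 53% |

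The power column applies when the high-dose cohort has the higher prevalence. With equal prevalence of 5% to 30% and g = 1.0, type I error stays at 4.9% to 5.1%.

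**3. Chance imbalance.** If both cohorts sample one population, the probability that they differ by 4 or more seropositives is 1.3% at 5% prevalence, 6.3% at 10% and 23% at 30%. Such gaps do not inflate the type I error, which averages over them, but they would affect how one trial's result is read.

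**4. Cost and gain of adjustment.** With one covariate there are 37 error df, and the average variance factor is (1 − R²) × 37/36, taking the same titre distribution in both cohorts. At R² = 0 the detectable difference is (2.026 + 0.851) × 0.316 × √(37/36) = 0.92 SD. Multiplying by √(1 − R²) gives 0.90 at R² = 0.05, 0.87 at 0.10 and 0.82 at 0.20, against 0.91 unadjusted. The R² values are assumptions.

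**5. Why a continuous titre.** At 5% prevalence, the chance that a group of 20 has no seropositive participant is 0.95²⁰ = 36%, and that all 40 have none is 0.95⁴⁰ = 13%. At 10%, two per group are expected (20 × 0.10); one responder among two has an exact 95% interval of 1.3% to 98.7%. A positive/negative covariate, or responder rates within serostatus, would rest on very few people.

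**The case against.** The case for leaving the plan alone is substantial. Staged cohorts are the safety mechanism of a dose-escalation trial, safety is primary, immunogenicity is secondary, and section 8.2.1 says the study is not necessarily powered for group differences. Both cohorts share one site, one catchment, one recruitment process and the same eligibility criteria, so a true prevalence gap is not something the documents suggest. Without a gap the t-test keeps its 5% level. All of this stands, and it limits the point to a modest one. It does not explain why 8.3.3 commits to a between-dose test without saying that the cohorts are non-randomised.

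Three stronger readings are tempting, and the documents do not support them:

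- A reader might infer that the protocol itself says cAd3 immunity blunts cAd3 responses. It does not. The reported blunting concerns Ad5 and rAd5. Section 1.2.2 likens the properties of cAd3 to those of Ad5, which makes the extension reasonable, but it remains an inference.
- A reader might infer that the screening result is never used. Section 9.1.1 says cAd3 antibody will be evaluated, Week 4 vector antibody is a secondary objective, and a change-from-baseline test of it needs a pre-vaccination value. What is missing is a role in the between-dose comparison of GP responses.
- A reader might infer that adjustment always improves precision. At low prevalence it does not: with R² near zero it costs about 0.01 SD.

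**Conclusion.** The point holds as a modest improvement to the analysis plan. The GP ELISA and ICS dose contrasts are unadjusted, are confounded with enrolment order, and make no stated use of a relevant baseline value that is already collected. If cAd3 immunity is as uncommon and low in titre as the background says, the effect is small. It becomes material only if seroprevalence in Kampala is substantial and differs between the cohorts. The 6% to 9% error rates depend on the assumed 10% against 30% gap and on blunting of 0.5 to 1.0 SD; they are illustrations and not the expected error rate of this trial. The reason to act is that the safeguard is cheap and the contrast has no protection from randomisation.

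**What to change.** In section 8.3.3:

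1. Add a linear model of the log-transformed Week 4 response (GP ELISA and ICS) on dose group and continuous log10 baseline cAd3 neutralising titre, at least as a pre-specified sensitivity analysis beside the t-test. Name the screening sample as the baseline, and state how titres below the assay limit are coded.
2. Tabulate baseline cAd3 titre by dose group.
3. State that every between-dose contrast, including Barnard's test on responder rates, compares sequential, non-randomised cohorts.

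Do not use a positive/negative covariate or serostatus-stratified responder rates.

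The cost is wording and one degree of freedom, with no new sample or visit. The 0.01 SD cost is an average for cohorts with the same titre distribution; it is larger if they differ, because dose and covariate are then correlated, but that is also when the unadjusted test is exposed to bias. If nearly all titres fall at the assay limit, the covariate carries little information and the table will show it. Adjustment addresses this one measured factor and does nothing for other calendar-time or recruitment differences, so the non-randomised label is needed whatever the model shows.
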